### 9.6. Data Management

All source data will originate via existing data collection practices of the data custodians in Denmark, France, and Sweden. Linkage across different data banks (e.g., registries) within a database (e.g., Danish registries) will be implemented either by a country investigator or by a data custodian, in accordance with the country-specific practices and rules. The investigators in each country will use the source data to create the analytic dataset.

Details on data management will be provided in the SAP. Briefly, data accruing in the routine databases undergo database-specific quality control, subject to data custodians' internal process in each country, which, as a rule, is a government agency (National Health Data Board in Denmark, SNDS in France, National Board of Health in Sweden). Databases in all three countries have been recently characterized in a EMA-commissioned study titled Strengthening Use of Real-World Data in Medicines Development: Metadata for Data Discoverability and Study Replicability (EUPAS39322, (50)). This study was part of the EMA Big Data Initiative. The specific steps of data management taken by investigators to define the analytic dataset from the source data will vary by country. Generally, this will entail the following main steps:

- Obtaining approvals and completing protocol-specific data applications.
- Retrieval of or access to the protocol-specific source data. Retrieval or access is administered by an appropriate data authority in each country.
- Data management to prepare the analysis dataset according to specifications in the SAP by transforming the original routinely collected data to coded data in order to define analysis populations and study variables.
- Data cleaning and checking for consistency by plausibility ranges, units of measurement, and relevance of clinical information. Implausible values will be set to missing. Imputation of missing values is not planned.
- Generation of aggregate-level country-specific SAP-specified output in a computer readable format according to the data template prepared at the principal investigator institution.

PFIZER CONFIDENTIAL

CT24-WI-GL02-RF02 5.0 Non-Interventional Study Protocol Template For Secondary Data Collection Study 01-Aug-2023 Page 29 of 47 The principal investigator institution (Aarhus University) will use the country-specific aggregate data supplied via the data template (using Microsoft Excel or similar standard software) to generate output as appropriate per planned Tables, Listings and Figures, which will be specified in the SAP.

Approaches to federated analysis (common data models and/or scripts) may be considered if practical. The investigators will use either SAS or R software, in the most recent version available to their organizations at the time of the analyses. Individual-level data will not travel across country borders and will not be pooled.

# 9.7. Data Analysis

Detailed methodology for summary and statistical analyses of data collected in this study will be documented in a SAP, which will be dated, filed, and maintained by the sponsor. The SAP may modify the plans outlined in the protocol; any major modifications of primary endpoint definitions or their analyses would be reflected in a protocol amendment. Data will be analysed and reported separately in each country. If relevant, meta-analysis of countryspecific results for the exploratory objective may be considered.

# 9.7.1. Descriptive Analysis

Distributions of the descriptive characteristics of patients with AA will be reported by exposure cohort, using appropriate summary statistics: counts and proportions for categorical variables, and means and standard deviations (or median with interquartile range (IQR), where appropriate) for continuous variables.

# 9.7.2. Analyses of the Primary Objectives

The primary analysis will comprise estimation of IRs with 95% CIs for the safety events of interest using a time-to-event analysis (except the growth metrics, which will be reported using means, medians or percentiles as appropriate). The analyses will include:

- Total number of patients in each exposure cohort
- Number of each new safety event of interest observed during the follow-up time in each exposure cohort
- Crude IRs (and cumulative incidences over selected prespecified periods) of the safety events of interest and 95% CIs in each exposure cohort
- Age- and sex-standardized IRs and 95% CIs in each exposure cohort

The summary of event rates will report time to first event since index date for each exposure cohort with appropriate censoring rules applied for those who do not experience an event by the end of the follow-up period, including those who die and those who emigrate. Rates will be expressed as events/10,000 person-years (PYs) of follow-up or a larger denominator if appropriate.

### PFIZER CONFIDENTIAL

CT24-WI-GL02-RF02 5.0 Non-Interventional Study Protocol Template For Secondary Data Collection Study 01-Aug-2023 Page 30 of 47 The index date and follow-up period will be considered separately with respect to acute-onset outcomes (thromboembolic events, all infection endpoints, MACE) versus delayed outcomes (malignancy excluding NMSC, NMSC, fracture, the neurologic events of interest, MACE). IR and cumulative incidence of each endpoint will be computed after excluding patients with a respective prevalent condition. This lookback period to identify prevalent conditions may be shorter for acute-onset outcomes than for delayed outcomes. For events with long induction/latency period (e.g. malignancy, MACE), events during a prespecified post-index date period may be disregarded and considered prevalent, according to the hypothesized induction/latency periods. The endpoint MACE will be analysed using both approaches. Approaches with and without censoring at treatment discontinuation will be considered.

### 9.7.3. Analyses of the Exploratory Objective

An exploratory comparative analysis estimating hazard ratios of the safety events of interest among AA patients treated with ritlecitinib compared with patients treated with baricitinib or other systemic treatment will be conducted for the final report only, study size permitting. This analysis will use Cox's proportional-hazards regression to estimate HRs and 95% CIs. To account for potential confounding in the comparative analysis, a propensity-score based method, such as inverse-probability treatment weighting (IPTW) will be used to balance measured characteristics of the exposure cohorts being compared (51). The covariate balance between the exposure cohorts (before and after IPTW) will be evaluated using standardized differences for continuous covariates and standardized differences of proportion for each (non-missing) category for categorical covariates. Characteristics with standardized differences greater than 0.10 after weighting will indicate imbalance and will be adjusted for in the comparative analyses. If IPTW is applied, robust variance estimators will be used to address lack of independence between patients induced by weighting. The extent of unmeasured confounding will be assessed using the E-value method (52, 53). Full details of the methods will be provided in the SAP.

# 9.7.4. Subgroup Analyses

If study size permits, the following analyses will be conducted for the subgroups listed below: descriptive characteristics by exposure cohort, IRs by exposure cohort, and HRs for comparative analyses.

- Sex (male, female)
- Adolescent and adult populations, based on age on index date (12-17 years, 18 years and older)
- Prior systemic therapy
- To allow for sufficient follow-up for outcomes with long induction or latent periods, subgroup analyses will be conducted among the subset of patients with a minimum of 5 years of follow-up, defined as patients initiating the study treatments between 15 September 2023 and 14 September 2028.

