# 9.1.1. Study Population and Study Period

The study population will include eligible patients (described in Section 9.2) with AA initiating ritlecitinib, baricitinib or other approved systemic AA treatments during the cohort accrual period. The cohort accrual period will include the first 8 years following ritlecitinib approval (15 September 2023 to 14 September 2031). The study period will include follow-up through 14 September 2033, to allow a minimum of 2 years of follow-up for the last patient accrued, given some longer-latency outcomes.

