# 9.1.2. Index Date and Follow-Up

The index date will be the date of the eligible initiation of ritlecitinib, baricitinib or another approved systemic treatment for AA during the cohort accrual period, as recorded in the data sources. Follow-up will start on the date after the index date and continue until the earliest of disenrollment from the data source, an event of interest, or censoring.

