### Figure 1. Study Design Schema

```
Cohort accrual period [15 September 2023 – 14 September 2031]
(First dispensing of ritlecitinib, baricitinib or another approved systemic AA treatment)
Day 0 = index date in a given exposure cohort
```

Diagnosis of Alopecia areata [-5 years, 0 days]	
Exclusion: age <12 years on index date [0, 0]	
Exclusion: minimal residence [-365 days, -1 day]	
Washout period to define new users [-5 years, -1 day]	
	Follow up Window Days (1, Censor a ]

a. Earliest of: outcome of interest, or censoring by discontinuation/switch, death, disenrollment, end of the study period on 15 September 2033.

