### 9.3. Variables

### 9.3.1. Exposure

Exposure cohorts will be defined based on the type of treatment dispensed on the index date. The following 3 exposure cohorts will be defined:

- 1. Ritlecitinib cohort
- 2. Baricitinib cohort
- 3. Other approved systemic AA treatment cohort (if used)

The eligible treatment initiated on the index date will be referred to as the index treatment. The exposure will continue until the end of a 90-day grace period following the estimated discontinuation of the index treatment. Discontinuation may result either by stopping the index treatment or initiation (switching to) another study treatment. Duration of each dispensing will be computed based on days supplied, estimated based on assumed daily dose, package size, and number of packages in each dispensing. Dispensings less than 90 days apart will represent a continuous treatment period. Definitions, including duration of the grace period, may be slightly modified if otherwise indicated by the data.

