With an estimated 835 ritlecitinib-exposed patients accrued over 8 years (Table 2), and with a 10-year study period, the expected number of observed PYs will be 0\*9 + 74\*8 + 96\*7 + 110\*6 + 127\*5 + 144\*4 + 161\*3 + 123\*2 = 3,864, assuming no lost to follow-up. A 1:1 ratio of ritlecitinib:comparator patients would yield a total of 7,728 PYs and an expected number of events of 9, 10, and 15 for the endpoints malignancy, thromboembolic events, and serious infections during follow-up. In this setting, there would be sufficient power to detect a minimum HR of 6.7, 6.4, and 4.3 for the endpoints malignancy, thromboembolic events, and serious infections (or other outcomes of similar incidence). However, the analysis will be conducted separately by data source and each individual data source is unlikely to accrue 835 ritlecitinib-exposed patients.

Minimum detectable HRs will be lower for the subgroup analysis of patients with a minimum of 5 years of follow-up (during the 10-year study period). 407 ritlecitinib-exposed patients

PFIZER CONFIDENTIAL

CT24-WI-GL02-RF02 5.0 Non-Interventional Study Protocol Template For Secondary Data Collection Study 01-Aug-2023 Page 28 of 47 accrued over 5 years (Table 2), assuming a 1:1 ratio and no lost to follow-up, would provide sufficient power to detect minimum HRs of 10.3, 9.9, and 6.1 for the endpoints malignancy, thromboembolic events, and serious infections.

Of note, it is possible that the comparator groups may be larger than the ritlecitinib group, given baricitinib's earlier approval date and the potential inclusion of other EU approved systemic treatments. If patients are receiving baricitinib at a substantially higher rate than ritlecitinib (e.g., a ratio of 2:1 or greater), then the minimum detectable hazard ratios could be met with fewer ritlecitinib-exposed patients.

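### The subgroup labelled as having five years of follow-up secures only potential follow-up, and restricting to it adds no late person-time for long-latency outcomes

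*Protocol*

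**What the plan says.** Protocol section 9.7.4 gives the reason for the subgroup, "To allow for sufficient follow-up for outcomes with long induction or latent periods", and defines its members as "patients with a minimum of 5 years of follow-up, defined as patients initiating the study treatments between 15 September 2023 and 14 September 2028". Incidence rates and, study size permitting, hazard ratios are to be produced for it. Section 9.5 gives its size as 407 ritlecitinib patients, with minimum detectable hazard ratios of 10.3, 9.9 and 6.1 for malignancy, thromboembolic events and serious infections.

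On the length of follow-up, section 9.1.1 states: "The study period will include follow-up through 14 September 2033". Section 9.1.2 has each patient's follow-up "continue until the earliest of disenrollment from the data source, an event of interest, or censoring", and the footnote to Figure 1 spells this out: "Earliest of: outcome of interest, or censoring by discontinuation/switch, death, disenrollment", or the end of the study period. Under section 9.3.1, "The exposure will continue until the end of a 90-day grace period following the estimated discontinuation of the index treatment".

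Section 9.7.2 says that analyses which do and do not censor when treatment stops will both be considered. It ties neither to this subgroup. It also allows early events to be disregarded for outcomes with long latency. Section 9.7.5 implies a 12-month minimum induction period for malignancy in the main analysis, with 6 months as the sensitivity value.

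**The concern.** The label describes something that the definition does not deliver. Starting treatment before 15 September 2028 guarantees that the calendar leaves five years before the study closes. It does not guarantee that a patient is observed for five years.

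The restriction also does not serve its stated purpose well. Late person-time comes only from patients who entered early, and the full cohort already contains all of them. Removing later entrants leaves late person-time unchanged and takes away their contribution at intermediate lags. A single rate or hazard ratio over all time since entry then averages early and late experience.

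What is at stake is interpretation. A low or null subgroup rate on malignancy or neurodegenerative disease could be read as five-year evidence on latency when it is mostly not that.

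**Working it through.** **Inputs.** Expected eligible entrants by accrual year (Table 2): 0, 74, 96, 110, 127, 144, 161, 123. Years of follow-up per accrual year (section 9.5): 9, 8, 7, 6, 5, 4, 3, 2, with no loss. Background rates per 1,000 PYs (Table 3): malignancy excluding NMSC 1.13, thromboembolic events 1.17, serious infections 1.89. Allocation is 1:1. The protocol does not state alpha or power; I assume two-sided 0.05 and 80%.

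**Step 1: potential follow-up.** From 14 September 2028 to 14 September 2033 is 1,826 days, or 5.0 years. The label is correct for potential follow-up.

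**Step 2: reproduce the plan's figures.** PYs = sum of entrants × years.
- Full cohort: 592 + 672 + 660 + 635 + 576 + 483 + 246 = 3,864, as stated.
- Subset (accrual years 1 to 5, 407 patients): 592 + 672 + 660 + 635 = 2,559.

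Events in both arms = 2 × PYs × rate / 1,000. Minimum detectable HR = exp(2 × (1.960 + 0.842) / √events), the Schoenfeld formula.

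| | Full cohort: events, HR (stated) | Subset: events, HR (stated) |
|---|---|---|
| Malignancy | 8.73, 6.66 (6.7) | 5.78, 10.28 (10.3) |
| Thromboembolic events | 9.04, 6.45 (6.4) | 5.99, 9.87 (9.9) |
| Serious infections | 14.61, 4.33 (4.3) | 9.67, 6.06 (6.1) |

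The subgroup figures are reproduced using all person-time from entry with complete potential follow-up. The plan therefore sized the subgroup as a pooled analysis with no censoring. (Section 9.5 says the detectable ratios will be lower in this subgroup, but its own figures are higher; that is a separate point.)

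**Step 3: split person-time at a lag L.** PYs beyond L = sum of entrants × max(years − L, 0).

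| Lag | Subset | Full cohort | Difference |
|---|---|---|---|
| 12 months | 2,559 − 407 = 2,152 | 3,864 − 835 = 3,029 | 877 |
| 2 years | 2,559 − 814 = 1,745 | 3,864 − 1,670 = 2,194 | 449 |
| 5 years | 74×3 + 96×2 + 110×1 = 524 | 524 | 0 |

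On these whole-year weights the full cohort has more late person-time at every lag under 4 years and the same amount from 4 years on. At no lag does the subset have more. Of the subset's person-time, 524 / 2,559 = 20.5% lies beyond year 5, against 524 / 3,864 = 13.6% in the full cohort. If entry is placed at mid-year instead, both groups hold 727.5 PYs beyond year 5, so the conclusion is unchanged.

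**Step 4: late events.** 524 × 1.13 / 1,000 = 0.59 expected malignancies beyond year 5 in the ritlecitinib cohort, all countries together.

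**Step 5: how far observed follow-up could fall short.** The protocol gives no censoring rate. Assuming a constant annual rate of 1%, 5%, 10%, 20% or 30%, the share of members still followed at 5 years is 95%, 77%, 59%, 33% or 17%.

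**The case against.** Several stronger readings are tempting, and the protocol does not support them.

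- *The subgroup was meant to look beyond the first five years, and about 80% of its person-time falls short of that.* The share is right (2,035 / 2,559 = 79.5%, or 74% with mid-year entry), but section 9.7.4 asks only for sufficient follow-up and names no five-year period to be passed. The only induction period named is 12 months, for malignancy. On that basis 407 / 2,559 = 15.9% of subset time is early.
- *Latency is otherwise ignored.* Section 9.7.2 allows a lag and plans cumulative incidence over prespecified periods, and section 9.7.5 varies the malignancy lag. The subgroup is one size-conditional analysis among these.
- *Members will be censored when treatment stops.* Figure 1 says so, but section 9.7.2 leaves the choice open. Section 9.7.5 lists the analysis without such censoring as a sensitivity analysis for acute-onset events only, which suggests that delayed outcomes may not be censored at discontinuation in the main analysis. With the minimal loss expected in section 9.2, most members would then reach five years.
- *Data are thrown away.* The full-cohort analysis stays; the subgroup is additional.
- *Selection by entry date is itself the mistake.* It is the sound choice. Selecting on observed five-year follow-up would condition on surviving event-free.

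It can also fairly be said that the label is readable as potential follow-up, since the entry dates stand in the same sentence, and that the restriction raises the beyond-year-5 share from 13.6% to 20.5%. Both are true. Neither creates late person-time that the full cohort lacks, and neither lets a pooled estimate separate early from late risk.

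**Conclusion.** The point holds in a limited form. The label promises observed follow-up where the definition secures only potential follow-up, and the restriction adds no late information: 524 PYs beyond year 5 with or without it, and 877 fewer beyond 12 months with it. A pooled subset rate or hazard ratio cannot show change with time since initiation.

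The person-year figures rest on the protocol's projected uptake, whole-year weights and no loss. Censoring would lower them, but the subset could still not exceed the cohort that contains it. The statistical analysis plan may settle the censoring approach; the entry window and label are fixed in the protocol itself. No primary result is put at risk. This is a cheap improvement to a secondary analysis whose subject is long-latency safety.

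**What to change.** 1. For the delayed outcomes of section 9.7.2, add whole-cohort incidence rates in a few prespecified windows of time since initiation, consistent with the induction lag in sections 9.7.2 and 9.7.5. Every patient contributes to each window reached. As an illustration, up to 1 year, over 1 to 5 years and beyond 5 years would hold 835, 2,505 and 524 ritlecitinib PYs on the protocol's weights, or about 0.9, 2.8 and 0.6 malignancies at 1.13 per 1,000 PYs.
2. Keep the entry-date subset only under the label *at least 5 years of potential follow-up*. State which censoring approach applies to it, and report its observed follow-up (for example the median and the proportion followed for 5 years).
3. Do not select on observed five-year follow-up.

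The cost is wording plus splitting of person-time in data already planned; no new data are needed. The downside is sparse late windows. Results are analysed by country without pooling of individual data (sections 9.6 and 9.7), and counts of 1 to 4 may be masked (section 9.10). Some late cells will therefore be empty, masked or very imprecise, so windows should be few and the estimates read as descriptive.

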### PFIZER CONFIDENTIAL

CT24-WI-GL02-RF02 5.0 Non-Interventional Study Protocol Template For Secondary Data Collection Study 01-Aug-2023 Page 31 of 47 • Subgroups may be considered based on ritlecitinib dose and duration

# 9.7.5. Sensitivity Analyses

A number of sensitivity analyses will be performed as listed below. Each sensitivity analysis will aim to examine the robustness of the findings given certain assumptions about the analysis. Each sensitivity analysis will be performed on the entire study population and, with the exception of the analysis parameter that is being altered, will use all main analysis procedures:

- Re-estimating the IRs and HRs with shorter grace periods for defining treatment discontinuation/switch: e.g., zero days and 30 days
- Re-estimating the IRs and HRs for acute-onset events using an intention-to-treat (ITT)-like approach, whereby follow-up will not be censored by treatment discontinuation
- Re-estimating the IRs and HRs for malignancy excluding NMSC and NMSC, using 6 months instead of 12 months after treatment initiation as the minimum induction period
- Re-estimating the IRs and HRs among patients without a record of rheumatoid arthritis, atopic dermatitis, or juvenile idiopathic arthritis on or before index date
- Re-estimating the IRs and HRs for MACE using an alternative definition

# 9.8. Quality Control

Investigators in the respective countries will be responsible for following the internal standard operating procedures to ensure data quality and integrity, including archiving of statistical programs, appropriate documentation of data cleaning and management.

The Department of Clinical Epidemiology, Aarhus University has implemented a series of internal standard operating procedures for data management and analysis as well as staff training. At a minimum, all study documents are reviewed by a senior epidemiologist and a statistician as well as by the entire research team. A senior epidemiologist will supervise the project and review the output before submission to the MAH and the regulator. Clinical expertise is available for appropriate interpretation of results. All project staff members receive comprehensive orientation training and are regularly trained.

The BPE has implemented a quality management system for all its activities and is certified ISO 9001:v2015 for its activities in pharmaco-epidemiology research. CNAM data extraction will be validated using the expected population size estimated using the SNDS. All statistical logs are kept and can be provided. In the case of interim analyses, the database for the interim analysis is locked and kept for ulterior validation if needed. Independent double programming will be performed for the main criteria and analysis, and the results compared for validation.

